### Objective Response Rate

The trial does not allocate initial alpha to ORR. ORR will be formally tested only if the hypotheses for PFS and OS are significant. The testing of ORR will be based on the first 352 subjects enrolled in the trial. If the null hypotheses for OS and PFS are rejected at IA1 or at a time later than IA1, the p-value of ORR from the IA1 analysis will be compared to an  $\alpha$ -level of 0.025. Power at the possible  $\alpha$ -level as well as the approximate treatment difference required to reach the bound ( $\Delta$ ORR) are shown in [Table 17](#), assuming underlying 50% and 70% response rates in the control and experimental groups, respectively.

Table 17 Possible Alpha-levels and Approximate ORR Difference Required to Demonstrate Efficacy for ORR

$\alpha$	$\sim\Delta\text{ORR}$	Power
0.025	0.1002	0.9719

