## **8.6 Statistical Methods**

### **8.6.1 Statistical Methods for Efficacy Analyses**

This section describes the statistical methods that address the primary and secondary objectives. Methods related to exploratory objectives will be described in the sSAP.

Efficacy results that will be deemed to be statistically significant after consideration of the Type I error control strategy are described in Section 8.8. Nominal p-values will be computed for other efficacy analyses, but should be interpreted with caution due to potential issues of multiplicity.

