### 8.6.1.3 Objective Response Rate

The ORR is defined as the proportion of subjects who achieve a best objective response of PR or CR.

Stratified Miettinen and Nurminen’s method will be used for comparison of ORR between the treatment groups. The difference in ORR and its 95% CI from the stratified Miettinen and Nurminen method with strata weighting by sample size will be provided. The same stratification factors used for randomization (see Section 5.4) will be used as stratification factors in the analysis.

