ORR (RECIST 1.1*) by BICR	Testing: Stratified Miettinen and Nurminen method	ITT	Subjects with missing data are considered non-responders
DOR (RECIST 1.1*) by BICR	Summary statistics using Kaplan-Meier method	All responders in ITT	Non-responders are excluded in analysis
*As assessed by BICR per RECIST 1.1 modified to follow a maximum of 10 target lesions and a maximum of 5 target lesions per organ			

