## 8.9 Sample Size and Power Calculations

Four hundred and thirty subjects were planned to be randomized in 1:1 ratio into pembrolizumab+EP and the saline placebo+EP arms. By the time of the current amendment, 453 subjects were enrolled for this study.

The final PFS analysis for the study will occur about 22 months from study start. If 387 PFS events occur by the time of the final PFS analysis, the study will have a power of 96% approximately to demonstrate a HR of 0.65 on PFS at initially allocated  $\alpha=0.006$ .

The final OS analysis will occur when at least 294 events have occurred or approximately 31 months from study start, whichever occurs later. With a minimum of 294 events at the time of final analysis, the study has at least 94% power to demonstrate a HR of 0.65 on OS at initially allocated  $\alpha=0.019$ .

The above power calculations for OS and PFS are based on the following assumptions: 1) 453 subjects were enrolled over 14.5 months following the actual enrollment pattern; 2) median PFS is 4.3 months in the control arm and HR is 0.65; 3) median OS is 10 months in the control arm and HR is 0.65; 4) The exponential dropout rates assumed for OS and PFS are 1% per month.

The sample size and power calculations were performed in the software R (package “gsDesign”).

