### **3.5 STATISTICAL METHODS**

This section describes the statistical methods that address the primary, secondary and exploratory objectives as stated in the protocol.

Statistical methods for efficacy analyses are described in Section 3.5.1. Statistical testing and inference for safety analyses are described in Section 3.5.2. Efficacy results that will be deemed to be statistically significant after consideration of the Type I error control strategy are described in Section 3.7, Multiplicity. Nominal p-values may be computed for other efficacy analyses as a measure of strength of association between the endpoint and the treatment effect rather than formal tests of hypotheses.

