### 3.5.1.4 Duration of Response (DOR)

For subjects who demonstrate CR or PR, DOR is defined as the time from first documented evidence of CR or PR until disease progression or death due to any cause, whichever occurs first. Censoring rules for DOR are summarized in [Table 2](#). DOR will be assessed using RECIST 1.1 by BICR.

For each DOR analysis, a corresponding summary of the reasons responding subjects are censored will also be provided. Subjects who are alive, have not progressed, have not initiated new anti-cancer treatment, have not been determined to be lost to follow-up, and have had a disease assessment within ~5 months of the data cutoff date are considered ongoing responders at the time of analysis. If a subject meets multiple criteria for censoring, the censoring criterion that occurs earliest will be applied.

Table 2 Censoring Rules for DOR

Situation	Date of Progression or Censoring	Outcome
No progression nor death, no new anti-cancer therapy initiated	Last adequate disease assessment	Censor (non-event)
No progression nor death, new anti-cancer therapy initiated	Last adequate disease assessment before new anti-cancer therapy initiated	Censor (non-event)
Death or progression after $\geq 2$ consecutive missed disease assessments	Last adequate disease assessment prior to $\geq 2$ missed adequate disease assessments	Censor (non-event)
Death or progression after $\leq 1$ missed adequate disease assessments	Progressive disease or death	End of response (Event)
A missed disease assessment includes any assessment that is not obtained or is considered inadequate for evaluation of response.		

[Table 3](#) summarizes the key efficacy analyses.

Table 3 Efficacy Analysis Methods for Primary and Secondary Efficacy Endpoints

Endpoint/Variable (Description, Time Point)	Statistical Method	Analysis Population	Missing Data Approach
Primary Analyses:			
PFS (RECIST 1.1) by BICR	Testing: Stratified Log-rank test Estimation: Stratified Cox model with Efron's tie handling method	ITT	Censored according to rules in Table 1
OS	Testing: Stratified Log-rank test Estimation: Stratified Cox model with Efron's tie handling method	ITT	Censored at last known alive date
Secondary Analyses:			
ORR (RECIST 1.1) by BICR	Stratified Miettinen and Nurminen method	ITT	Subjects with missing data are considered non-responders

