### 3.6 INTERIM ANALYSES

Two interim efficacy analyses are planned for this study.

- The first interim analysis (IA1) will be performed approximately 18 months from study start, 3.5 months after the last patient was enrolled. PFS and OS will be evaluated at IA1. ORR p-value from IA1 may be evaluated for statistical significance if PFS and OS null hypotheses are rejected at IA1 or at a later analysis time.
- The second interim analysis (IA2) will be performed approximately 22 months from study start, 7.5 months after the last patient was enrolled. The second interim analysis evaluation of OS and the final evaluation of PFS will be performed at this time.
- The final analysis will evaluate OS only. It is planned when a minimum of 294 deaths have been observed or approximately 31 months after first subject enrolled, whichever occurs later.

[figure not shown]
In addition to the formal efficacy analyses, the DMC will conduct regular safety monitoring, the timing of which is specified in the DMC charter. Decisions to stop the trial early will be based on DMC recommendations with review by the EOC.

Type I error control for the efficacy analyses as well as efficacy bounds are described in the next section.

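### Is it a fault that the formal ORR test uses the first 352 subjects while the efficacy tables list ITT for ORR?

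*Combined protocol and SAP*

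**What the plan says.** Protocol Section 8.8 (Objective Response Rate) and sSAP Section 3.7 carry the same sentence: "The testing of ORR will be based on the first 352 subjects enrolled in the trial". Both add that ORR gets no initial alpha, that it is tested only if PFS and OS are both rejected, and that the p-value used is the one from IA1, compared with 0.025. Protocol Table 17 and sSAP Table 9 give power 0.9719 and a required difference of about 0.1002 at true rates of 50% and 70%.

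The ORR row of protocol Table 13 reads "Testing: Stratified Miettinen and Nurminen method", with ITT in the population column. The ORR row of sSAP Table 3 also lists ITT and handles missing data this way: "Subjects with missing data are considered non-responders". Section 8.6.1.3 plans "The difference in ORR and its 95% CI from the stratified Miettinen and Nurminen method" and names no subset.

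On which statement governs, Section 8.6.1 refers significance claims under Type I error control to Section 8.8 and says of the rest: "Nominal p-values will be computed for other efficacy analyses". sSAP Section 3.5 does the same with reference to its Section 3.7: "Nominal p-values may be computed for other efficacy analyses as a measure of strength of association".

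On timing, Section 8.9 states that "453 subjects were enrolled over 14.5 months following the actual enrollment pattern". sSAP Section 3.6 places IA1 about 18 months from study start, "3.5 months after the last patient was enrolled".

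**The concern.** Read side by side, a table row labelled as testing with population ITT and a multiplicity section limited to 352 subjects seem to define two test sets for the key secondary endpoint. Each set has its own p-value and critical difference, so an observed difference between about 0.088 and 0.100 could be significant in one and not in the other. If the set were chosen after seeing the data, the one-sided error would exceed 0.025.

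The restriction also looks wasteful. It drops 453 − 352 = 101 randomized subjects (101/453 = 22.3%) with no stated reason, although on the planned timing every subject has about 3.5 months of follow-up at IA1.

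**Working it through.** **Inputs.** From the documents: 352 subjects in the formal test (Section 8.8), 453 randomized (Section 8.1), 1:1 allocation (Section 5.3), one-sided alpha 0.025 and rates of 50% and 70% (Section 8.8). Unstratified normal approximation; z = 1.96.

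**1. Which N lies behind Table 17?** With n per arm and mean rate 0.60:

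- Critical difference, pooled: 1.96 × √(2 × 0.6 × 0.4 / n)
- SE under the alternative: √((0.5 × 0.5 + 0.7 × 0.3)/n) = √(0.46/n)
- Power: Φ((0.20 − critical difference)/SE)

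For n = 176 the critical difference is 1.96 × √(0.48/176) = 0.1024 and the SE is √(0.46/176) = 0.0511. Power is Φ((0.20 − 0.1024)/0.0511) = Φ(1.91) = 0.9719, as in Table 17. The tabulated 0.1002 is the unpooled form, 1.96 × 0.0511. Both figures rest on 352.

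**2. The same calculation on 453.** For n = 226.5 the critical difference is 1.96 × √(0.48/226.5) = 0.0902 and the SE is √(0.46/226.5) = 0.0451. Power is 0.9926, and the unpooled critical difference is 0.0883. Table 17 cannot have been computed on 453.

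| Set | Power, 50% vs 70% | Critical difference (unpooled) |
|---|---|---|
| First 352 | 97.2% | 0.1002 |
| All 453 | 99.3% | 0.0883 |

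The gain is 2.1 percentage points. The standard error would fall by 1 − √(352/453) = 11.9%.

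**3. Is the test valid?** Membership of the first 352 is fixed by order of enrolment, so it does not depend on response or on assigned treatment. The comparison within that set is randomized and keeps its level of 0.025.

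**4. Can the sponsor choose between sets?** The statistics from nested sets of 352 and 453 correlate at √(352/453) = 0.88. Taking whichever is significant would give a one-sided error of about 3.6%. The plan closes that route: Section 8.8 and sSAP 3.7 fix the set and the analysis time, and Section 8.6.1 and sSAP 3.5 make any other ORR p-value nominal.

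**5. How mature are the omitted data?** At 4.348 weeks per month, the last subject has 3.5 × 4.348 = 15.2 weeks at IA1. Scans are due at Weeks 6 and 12 (±7 days), then Week 18, and a response needs confirmation at least 4 weeks later (Section 7.1.2.7.2). A Week 6 response can be confirmed at Week 12. A response first seen on the nominal Week 12 date cannot be confirmed before Week 16, which the last subject has not reached. Under uniform accrual (an assumption; the enrolment pattern is not shown), subject 352 enters at 14.5 × 352/453 = 11.27 months and has 6.73 months, about 29 weeks, at IA1.

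Uniform accrual is 453/(14.5 × 4.348) = 7.185 subjects per week. Those short of Week 18 number (18 − 15.22) × 7.185 = 20. Those short of Week 19, the end of the Week 18 window, number 27. If all 27 counted as non-responders, power on 453 would be 98.3%. About 46 such subjects would remove the advantage of 453, which is an extreme case because Week 6 responders confirmed at Week 12 still count.

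**The case for a change.** The strongest case for the concern is that ITT ordinarily means everyone randomized, that Table 13 labels the row as testing, and that neither table sends the reader to the 352 rule. All of that is true, and the documents give no reason for 352. Section 8.5.1 explains ITT as analysis in the randomized group, written for the primary endpoints. The first 352 can be analysed that way, but most readers would still take the table entry to mean 453. What stands is a missing cross-reference in a summary table. It does not create a second rule.

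The efficiency argument also has substance. The gain is small at 50% versus 70% only because power is already near its ceiling. At 50% versus 65%, an effect the documents do not assume, power is 81.5% on 352 and 90.0% on 453. The maturity argument for 352 is modest, since 453 keeps a small power advantage even with 27 late enrollees counted as non-responders. So one could reasonably have chosen 453.

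That does not make 352 wrong. Changing the set now would also have a cost. Section 8.0 requires a protocol amendment for key secondary methods. The 453-subject enrolment text is not among the changes listed for Amendment 09, which suggests that enrolment was complete by Amendment 08 (07-DEC-2018). IA1 would then fall by about 23-MAR-2019, before Amendment 09 (23-APR-2019). This is an inference: the list may not be exhaustive and IA1 timing is approximate. If it is right, the change would come at or after IA1 and would invite the question whether data prompted it.

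**Conclusion.** The concern is not sustained. The formal ORR test set is defined once, identically in both documents, in the sections that govern significance, and the stated power and critical difference are computed on it. Type I error is controlled at one-sided 0.025, and the test delivers its planned 97.2% power. The 3.6% error arises only if the sponsor departs from the written rule and picks the set after seeing results.

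Moving to 453 would be a trade-off: about 2 percentage points of power at the plan's own effect, on a test reached only after PFS and OS both succeed, against shorter follow-up for confirmed response in the latest enrollees. The PFS and OS conclusions are unaffected either way. A pointer from the tables to Section 8.8 and sSAP 3.7 would be clerical and change no result.

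This rests on the unstratified approximation that reproduces Table 17, on the planned IA1 timing and, for the late-enrollee counts and the follow-up of subject 352 only, on uniform accrual.

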## 8.9 Sample Size and Power Calculations

Four hundred and thirty subjects were planned to be randomized in 1:1 ratio into pembrolizumab+EP and the saline placebo+EP arms. By the time of the current amendment, 453 subjects were enrolled for this study.

The final PFS analysis for the study will occur about 22 months from study start. If 387 PFS events occur by the time of the final PFS analysis, the study will have a power of 96% approximately to demonstrate a HR of 0.65 on PFS at initially allocated  $\alpha=0.006$ .

The final OS analysis will occur when at least 294 events have occurred or approximately 31 months from study start, whichever occurs later. With a minimum of 294 events at the time of final analysis, the study has at least 94% power to demonstrate a HR of 0.65 on OS at initially allocated  $\alpha=0.019$ .

The above power calculations for OS and PFS are based on the following assumptions: 1) 453 subjects were enrolled over 14.5 months following the actual enrollment pattern; 2) median PFS is 4.3 months in the control arm and HR is 0.65; 3) median OS is 10 months in the control arm and HR is 0.65; 4) The exponential dropout rates assumed for OS and PFS are 1% per month.

The sample size and power calculations were performed in the software R (package “gsDesign”).

## 8.10 Subgroup Analyses and Effect of Baseline Factors

To determine whether the treatment effect is consistent across various subgroups, the between-group treatment effect for OS, PFS and ORR (with a nominal 95% CI) will be estimated and plotted within each category of the following classification variables:

- Stratification factors
  - Platinum chemotherapy (cisplatin, carboplatin)
  - LDH ( $\leq$ ULN,  $>$ ULN)
  - ECOG Performance Scale (0, 1)
- Age category ( $<65$ ,  $\geq 65$  years)

- Sex (female, male)
- Race (white, all others)
- Smoking status (former, current)
- Brain/liver metastasis status at diagnosis (yes, no)
- Region (East Asia, non-East Asia)
- Sites of metastasis at diagnosis (<3, ≥3)
- PD-L1 expression positive (TPS<1% vs ≥1%, CPS <1 vs ≥1)

### **8.11 Compliance (Medication Adherence)**

Drug accountability data for trial treatment will be collected during the study. Any deviation from protocol-directed administration will be reported.

### **8.12 Extent of Exposure**

Extent of exposure for a subject is defined as number of cycles in which the subject receives the study medication infusion. Summary statistics will be provided on extent of exposure for the ASaT population.

## **9.0 LABELING, PACKAGING, STORAGE AND RETURN OF CLINICAL SUPPLIES**

### **9.1 Investigational Product**

The investigator shall take responsibility for and shall take all steps to maintain appropriate records and ensure appropriate supply, storage, handling, distribution and usage of investigational product in accordance with the protocol and any applicable laws and regulations.

Clinical Supplies will be provided by the Sponsor as summarized in [Table 18](#). All other supplies not indicated in [Table 18](#) will be provided centrally by the Sponsor or locally by the trial site, subsidiary or designee, depending on local country operational or regulatory requirements. For any commercially available product that is provided by the trial site, subsidiary or designee every attempt will be made to source these supplies from a single lot/batch number.

Table 18 Product Descriptions

Product Name & Potency	Dosage Form	Source/Additional Information
Pembrolizumab 25 mg/mL (MK-3475)	Solution for Infusion	Provided centrally by the Sponsor
Carboplatin	Solution for Infusion	Provided centrally by the Sponsor or locally by the trial site, subsidiary, or designee. Product is not IMP
Cisplatin	Solution for Infusion	Provided centrally by the Sponsor or locally by the trial site, subsidiary, or designee Product is not IMP
Etoposide	Solution for Infusion	Provided centrally by the Sponsor or locally by the trial site, subsidiary, or designee Product is not IMP
Abbreviations: IMP=investigational medicinal product		

All supplies indicated in [Table 18](#) will be provided per the “Source/Additional Information” column depending on local country operational requirements.

Any commercially available product not included in [Table 18](#) will be provided by the trial site, subsidiary or designee. Every attempt should be made to source these supplies from a single lot/batch number. The trial site is responsible for recording the lot number, manufacturer, and expiry date for any locally purchased product as per local guidelines unless otherwise instructed by the Sponsor.

## 9.2 Packaging and Labeling Information

Clinical supplies will be affixed with a clinical label in accordance with regulatory requirements.

Open-label pembrolizumab will be provided in 2 vial kits. Open-label carboplatin, cisplatin, and etoposide will be provided as single-vial kits.

## 9.3 Clinical Supplies Disclosure

The pembrolizumab treatment in the trial is blinded but supplies are provided open label; therefore, an unblinded pharmacist or qualified trial site personnel will be used to blind

supplies. Trial treatment identity (name, strength or potency) is included in the label text; random code/disclosure envelopes or lists are not provided.

#### **9.4 Storage and Handling Requirements**

Clinical supplies must be stored in a secure, limited-access location under the storage conditions specified on the label.

Receipt and dispensing of trial medication must be recorded by an authorized person at the trial site.

Clinical supplies may not be used for any purpose other than that stated in the protocol.

#### **9.5 Discard/Destruction>Returns and Reconciliation**

The investigator is responsible for keeping accurate records of the clinical supplies received from the Sponsor or designee, the amount dispensed to and returned by the subjects and the amount remaining at the conclusion of the trial. For all trial sites, the local country Sponsor personnel or designee will provide appropriate documentation that must be completed for drug accountability and return, or local discard and destruction if appropriate. Where local discard and destruction is appropriate, the investigator is responsible for ensuring that a local discard/destruction procedure is documented.

#### **9.6 Standard Policies**

Trial site personnel will have access to a central electronic treatment allocation/randomization system (IVRS/IWRS system) to allocate subjects, to assign trial treatment to subjects and to manage the distribution of clinical supplies. Each person accessing the IVRS system must be assigned an individual unique PIN. They must use only their assigned PIN to access the system, and they must not share their assigned PIN with anyone.

### **10.0 ADMINISTRATIVE AND REGULATORY DETAILS**

#### **10.1 Confidentiality**

##### **10.1.1 Confidentiality of Data**

By signing this protocol, the investigator affirms to the Sponsor that information furnished to the investigator by the Sponsor will be maintained in confidence, and such information will be divulged to the institutional review board, ethics review committee (IRB/ERC) or similar or expert committee; affiliated institution and employees, only under an appropriate understanding of confidentiality with such board or committee, affiliated institution and employees. Data generated by this trial will be considered confidential by the investigator, except to the extent that it is included in a publication as provided in the Publications section of this protocol.

### **10.1.2 Confidentiality of Subject Records**

By signing this protocol, the investigator agrees that the Sponsor (or Sponsor representative), IRB/ERC, or regulatory authority representatives may consult and/or copy trial documents in order to verify worksheet/case report form data. By signing the consent form, the subject agrees to this process. If trial documents will be photocopied during the process of verifying worksheet/case report form information, the subject will be identified by unique code only; full names/initials will be masked prior to transmission to the Sponsor.

By signing this protocol, the investigator agrees to treat all subject data used and disclosed in connection with this trial in accordance with all applicable privacy laws, rules and regulations.

